This study involves the use of educational pamphlets and patient questionnaires, neither of which constitutes more than minimal risk for the patient. The decision to proceed with surgical intervention, as well as the choice of which surgery the subject undergoes, will be decided between the subject and primary surgeon prior to enrollment in the study. This particular study qualifies under the Expedited Category 7, which refers to research on individual or group characteristic or behavior or research employing survey, interview, oral history, focus group, program evaluation, human factors evaluation, or quality assurance methodologies. Additionally, this study qualifies under Category 5 of expedited review, as it entails a review of medical information, collected as part of clinical care, and not collected specifically for this protocol.

B. Risks and Discomforts

1. Describe and assess any reasonably foreseeable risks and discomforts — physical, psychological, social, legal or other. Include an assessment of their expected frequency (e.g., common – 65%, less common – 40%, unlikely – 5%, rare - <1%) and the seriousness (mild, moderate, severe).

Risks of the educational intervention of the study:

- Anxiety – unlikely (5%), mild
- Psychological harm (embarrassment) – unlikely (5%), mild
- Potential breach of confidentiality – rare (<1%), moderate

2. Discuss what steps have been taken and/or will be taken to prevent and minimize any risks/potential discomforts to subjects.

The primary intervention in this study is an educational intervention and is associated with minimal risk to the study subjects. Patients will have the opportunity to complete their preoperative and postoperative questionnaires in a private room, which helps reduce the risk of anxiety or psychological harm. Security provisions to protect confidential patient information will include the use of encrypted emails, password-protected data storage systems and storage of patient paper files in a locked room.

C. Potential Benefits

1. Describe the potential benefits subjects may expect to receive from participation in this study.

[] There is no direct benefit anticipated for the subjects.

Patients in the intervention arm will learn about appropriate storage and disposal patterns of opioid medications. Additionally, they will learn about side effects of opioid medications that they might not have otherwise been aware of. Conceivably any intervention that leads to a reduction of opioid consumption after surgery would help minimize the side effect profile and risks associated with these medications.

2. Specify the expected potential societal/scientific benefit(s) of this study.

The rates of substance abuse admissions and deaths attributable to prescription opioid abuse have significantly increased within the last ten years. Unused postoperative opioid medications are a source of opioids that may ultimately be diverted or misused by someone other than the surgical patient. The current literature indicates that a significant proportion of postoperative patients do not dispose of excess opioid medication and have even shared it with another person in the past. Educating surgical patients about the risks associated with opioid medications may help reduce opioid consumption, which has beneficial cost implications to society (reduced postoperative emergency room visits or urgent clinic visits). Educating surgical patients about appropriate storage and disposal of unused opioid medications would reduce the risk of opioid diversion to others who may be more likely to abuse these medications. Improved counseling of postoperative patients presents an opportunity to reduce opioid consumption and improve appropriate disposal of unused medications, both of which are beneficial for the society at large.

SECTION 8: ALTERNATIVES TO PARTICIPATION

Describe the alternatives to participation in the study available to prospective subjects. Include routine (standard of care) options as well as other experimental options, as applicable.

No alternatives exist. The only alternative to study participation is not to participate in the study.

There are routine standard of care alternatives available; specify:

There are other alternatives to study participation; specify:

SECTION 9: SUBJECT COSTS

1. Indicate below if subjects or their insurers will be charged for study procedures. Identify and describe those costs.

Not applicable: This study involves no interaction/intervention with research subjects.

This study involves interaction/intervention with research subjects; however there are no costs to subjects/insurers. The study interventions are being performed during standard preoperative and postoperative clinic visits that would have occurred even if the subject was not enrolled in the study.

This study involves interaction/intervention with research subjects, and there are costs to subjects/insurers:

2. If subjects or their insurers will be responsible for study-related costs, explain why it is appropriate to charge those costs to the subjects or their insurers. Provide supporting documentation as applicable (e.g., study procedures include routine (standard of care) procedures; FDA IDE/HDE/IND letter that supports billing to subjects).

Not applicable: The study involves no costs to subjects for study participation.

Study related costs will be billed to subjects or their insurers for the following reasons:

SECTION 10: SUBJECT COMPENSATION AND REIMBURSEMENT

1. If subjects will be compensated for their participation, explain the method/terms of payment (e.g., money; check; extra credit; gift certificate).

Not applicable: This study involves no interaction/intervention with research subjects.

No compensation will be provided to subjects.

Compensation will be provided to subjects in the form of cash/gift certificate.

Compensation will be provided to subjects in the form of a check issued to the subjects through the UCI Accounting Office. The subject's name, address, and social security number, will be released to the UCI Accounting Office for the purpose of payment and for tax reporting to the Internal Revenue Service (IRS).

Other:

2. Specify the schedule and amounts of compensation (e.g., at end of study; after each session/visit) including the total amount subjects can receive for completing the study.

Not applicable: This study involves no compensation to subjects.
Subjects will be compensated with the following schedule and amounts:

3. Specify whether subjects will be reimbursed for out-of-pocket expenses. If so, describe any requirements for reimbursement (e.g., receipt).

Not applicable: This study involves no reimbursement to subjects.
Subjects will be reimbursed; specify:

SECTION 11: CONFIDENTIALITY OF RESEARCH BIOSPECIMENS/DATA

A. Biospecimens/Data Storage

1. Indicate all subject identifiers that may be included with the biospecimens or collected for the research study.

This study does not involve the collection of subject identifiers.

Check all the following subject identifiers will be used, created, collected, disclosed as part of the research:

| | | |
|--|--|--|
|  Names |  Social Security Numbers |  Device identifiers/Serial numbers |
|  Dates |  Medical record numbers |  Web URLs |
|  Postal address |  Health plan numbers |  IP address numbers |
|  Phone numbers |  Account numbers |  Biometric identifiers |
|  Fax numbers |  License/Certificate numbers |  Facial Photos/Images |
|  Email address |  Vehicle id numbers |  Any other unique identifier |
|  Other (Specify all): | | |

Indicate how data will be stored and secured, including electronic data as well as hardcopy data paper records, electronic files, audio/video tapes, biospecimens, etc.

Electronic Data/Files (check all that apply):

- Anonymous data will be maintained; no subject identifiers
- Coded data; code key is kept separate from data in secure location.
- Data includes subject identifiable information. Provide rationale for maintaining subject identifiable info):
- Data will be stored on secure network server.
- Data will be stored on standalone desktop computer (not connected to network/internet)
- Other (specify here):

Hardcopy Data (Records, Recordings, Photographs) and Biospecimens (check all that apply):

- Anonymous biospecimens/data will be maintained; no subject identifiers
- Coded data; code key is kept separate from biospecimens/data in secure location.
- Biospecimens/Data includes subject identifiable information (Provide rationale for maintaining subject identifiable info):
- Data will be stored in locked file cabinet or locked room.
- Biospecimens will be stored in locked lab/refrigerator/freezer.
- Other (specify here):

2. List the location(s) where the data and/or biological specimens will be stored.

Data will be stored within file cabinets in locked rooms (offices of the co-investigators) at the UC Irvine Women's Clinic and Kaiser Permanente Orange County – Irvine Medical Center OB Gyn Clinic.

3. If subject identifiable data will be transported or maintained on portable devices, explain why it is necessary use these devices.

Not applicable: Research data will not be transported or maintained on portable devices.
Research data will need to be maintained on the following portable device(s) for the following reason(s):

B. Data and/or Biological Specimens Access

Specify who will have access to subject identifiable data and/or biological specimens as part of this study.

Not applicable: No subject identifiers will be collected.

Authorized UCI personnel such as the research team and appropriate institutional officials, the study sponsor or the sponsor's agents (if applicable), and regulatory entities such as the Food and Drug Administration (FDA), the Office of Human Research Protections (OHRP), and the National Institutes of Health (NIH).

Other:

C. Data and/or Biological Specimens Retention

Indicate how long subject identifiable data and/or biological specimens, including the subject code key will be retained.

Not applicable: No subject identifiable research data will be retained.

Separate code key will be destroyed or subject identifiable information will be removed from the biospecimens and/or data at the earliest convenience, consistent with the conduct of this research. Specify timeframe: Code key will be destroyed after the subjects have been identified within the UC Irvine electronic medical system and CURES 2.0 database 12 months after the initial surgery (to evaluate for additional opioid prescriptions).

Destroyed once research data is analyzed.

Destroyed after publication/presentation.

Will be maintained; specify time frame and provide the rationale:

Will be stored and maintained in a repository for future research purposes.

Will be retained for six years as this research involves Protected Health Information (PHI) (e.g., IRB documentation, consent/assent forms – NOT the actual PHI).

Will be retained for seven years after all children enrolled in the study reach the age of majority [age 18 in California] as this study includes children.

Will be retained 25 years after study closure as this study involves in vitro fertilization studies or research involving pregnant women.

Will be retained for two years after an approved marketing application, as this is a FDA regulated study. If approval is not received, the research records will be kept for 2 years after the investigation is discontinued and the FDA is notified.

Other:

D. Photographs, Audio/Video Recordings Retention

1. If subject identifiable audio or video recordings will be collected, specify the timeframe for the transcription and describe retention/destruction plans.

Not applicable: Subject identifiable audio/video recordings will not be collected.

Audio or video recordings transcribed; specify time frame:

Audio or video recordings will be maintained; specify time frame:

Audio or video recordings maintained indefinitely; provide the rationale:

Audio or video recordings destroyed; specify time frame:

2. If subject identifiable photographs will be collected, describe retention/destruction plans.

Not applicable: Subject identifiable photographs will not be collected.

Photographs will be maintained; specify time frame:

Photographs maintained indefinitely; provide the rationale:

Photographs destroyed; specify time frame:

E. Certificate of Confidentiality

1. Indicate whether a Certificate of Confidentiality (COC) has been or will be requested.

Not applicable: No COC has been requested for this study.

A COC will be or has been requested for this study.

A COC has been obtained for this study. The expiration date of this COC is:

2. Explain in what situations the UCI study team will disclose identifiable private information protected by a COC.

N/A

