The pattern of postoperative opioid consumption will be evaluated at 2 weeks and 6 weeks after the surgery and will be compared between subjects who underwent preoperative opioid education versus those who did not. The hypothesis is that subjects who receive the preoperative opioid education will be less likely to consume opioid tablets after 2 weeks compared to subjects who did not receive the educational intervention.

The rates of prescription refills 12 months after the surgery will be evaluated and compared between subjects who underwent preoperative opioid education versus those who did not. The hypothesis is that subjects who receive preoperative opioid education will be less likely to have opioid refills within the first 12 months postoperatively compared to subjects who did not receive the educational intervention.

The postoperative opioid consumption between subjects with particular clinical conditions (preoperative opioid use, active tobacco use, the presence of a chronic pain syndrome, anxiety, depression) will be compared to subjects without these conditions. The hypothesis is that subjects with these clinical conditions will have higher postoperative opioid consumption rates, including higher rates of opioid prescription refills within 12 months after surgery, compared to subjects without these conditions.

The subjects' opinions about the adequacy of their initial postoperative opioid prescriptions will be compared between subjects who received the preoperative educational intervention versus those who did not. The hypothesis is that subjects who received the preoperative educational intervention will be more likely to answer that their opioid prescription was "more than adequate" or "adequate" compared to subjects who did not receive the educational intervention. The subjects' opinions regarding the adequacy of their initial postoperative opioid prescriptions will be compared between subjects with particular clinical conditions (chronic pain syndromes, anxiety, depression, active tobacco use, and preoperative opioid use) to subjects without these conditions. The hypothesis is that subjects with the clinical conditions will be more likely to answer "less than adequate" regarding their postoperative opioid prescriptions compared to subjects without these clinical conditions.

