Inclusion criteria:

Female

| |
|---|
| 
Age 18-99 years old English speaking Evaluated by a provider within the Urogynecology division at UC Irvine or Kaiser Permanente Orange County – Irvine Medical Center and consented for either a uterosacral ligament suspension, sacrospinous ligament fixation, minimally-invasive colpopexy (either laparoscopic or robotic-assisted laparoscopic), colporrhaphy, or colpocleisis
 
Exclusion criteria: Non English-speaking Cognitive deficits that would prevent the patient from completing the study questionnaires Cancellation of the surgery Combined case with another surgical service (i.e. colorectal surgery)
 |
| 
2. If eligibility is based on age, gender, pregnancy/childbearing potential, social/ethnic group, or language spoken (e.g., English Speakers only), provide a scientific rationale.
 |
| 
The division of urogynecology at UC Irvine exclusively treats female patients with the above stated procedures for the indication of pelvic organ prolapse. As such, male patients would not be eligible to participate since they are not candidates for the above noted procedures due to anatomical differences. The study patient educational pamphlets are only available in English and therefore the study objectives are best observed within an English proficient patient population.
 |

SECTION 4: RECRUITMENT METHODS

| |
|--|
| 
Check any of the following methods that will be used to recruit subjects for this study:
 |
| 
 This study involves no direct contact with subjects (i.e., use of existing records, charts, specimens).
 
Specify database or IRB-approved protocol number (HS#), if applicable:
 |
| 
 Advertisements, flyers, brochures, email, Facebook, and/or other media.
 
Specify where recruitment materials will be posted:
 
If subjects will be recruited by mail, e-mail, or phone, specify how their contact information will be obtained:
 |
| 
 The study will be listed on Clinicaltrials.gov.
 |
| 
 The study will be listed on the UC Irvine Health Clinical Trials web page.
 |
| 
 The UCI Social Sciences Human Subjects Lab/Sona Systems will be used.
 |

| |
|--|

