10. Post-operative date that the patient passed a voiding trial and the transurethral catheter was removed
11. Duration of the surgery (in minutes)

C. Research Procedures

1. Provide a detailed chronological description of all research procedures.

The study concept would be introduced to the patients at the consult visit, preoperative visit, on in the preoperative unit prior to surgery. If the patient agrees to participation during any of these encounters, written consent and HIPPA authorization will be obtained and the patient would be randomized to the intervention or control arm using a computerized randomization scheme on REDCap. The randomization will be stratified by the site of the surgery (UC Irvine Medical Center versus Kaiser Permanente Orange County – Irvine Medical Center). If the patient is randomized to the intervention arm, the first opioid informational pamphlet will be provided and reviewed with the patient in addition to standard preoperative instructions. If the patient is randomized to the control arm, standard preoperative instructions will be provided. Patients within both arms of the study will receive standardized postoperative medication prescriptions prior to the surgery. Patients within both arms of the study will complete the modified surgical pain score and preoperative opioid education study survey prior to surgery.

After the surgery is completed, the primary surgeon will decide whether to admit the patient to the hospital and which postoperative analgesics will be administered within the hospital prior to discharge for subjects in both study arms. The patient will follow up for standard postoperative clinic visits at 2 weeks and 6 weeks postoperatively. One to two days prior to the 2 week postoperative visit, the patient will be contacted via telephone to remind her to bring her opioid prescription bottle to the clinic visit.

Between the surgery date and the 2 week postoperative visit, the electronic medical records will be reviewed to evaluate the length of the surgery, intraoperative complications, the postoperative date of discharge, the postoperative date of removal of the transurethral foley catheter, the total daily morphine equivalents that the patient was prescribed prior to discharge from the hospital, and the presence of opioid prescriptions 30 days prior to the surgery. Additionally, the CURES 2.0 Database will be queried to evaluate for opioid prescriptions 30 days prior to the surgery.

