5. Sample Size Determination: Explain how the overall target sample size was determined (e.g., power analysis; precision estimation), providing justification of the effect size for the primary outcome based on preliminary data, current knowledge/literature and/or cost consideration; if appropriate, provide sample size justification for secondary outcomes. Power analysis should (at least) match the primary outcome/endpoint.

A power calculation indicates that a sample size of 63 subjects in each arm is necessary to achieve 80% power to detect a mean difference of 5 opioid tablets consumed with a significance level of 0.05. This difference is equivalent to a difference of 0.5 SD. Given an anticipated attrition rate of 15%, 73 subjects will be recruited into each arm of the study. Current literature suggests that the mean number of opioid tablets consumed by patients undergoing urogynecologic surgeries for pelvic organ prolapse ranges between 2-13 tablets and therefore, this study is powered to detect a 50% decrease in postoperative opioid tablet consumption if we anticipate that patients who do not undergo the educational intervention will consume a mean of 10 tablets.

SECTION 7: RISK ASSESSMENT AND POSSIBLE BENEFITS

A. Risk Assessment

1. Indicate the appropriate level of review of this study, based upon your risk assessment.

This study involves greater than minimal risk to subjects and requires Full Committee review.

This study involves no more than minimal risk and qualifies as [Expedited research](#).

2. If this study involves no more than minimal risk, provide justification for the level of review and for all applicable Expedited Categories you have chosen.

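### The primary t-test ignores site and preoperative opioid use, although the trial stratifies on the first and expects the second to predict consumption; a prespecified adjusted model would gain precision at almost no cost

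*Combined protocol and SAP*

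**What the plan says.** - **Randomisation.** Sections 1.4, 6.B.1 and 6.C.1 name one balancing factor, the medical centre: "The randomization will be stratified by the site of the surgery".
- **Eligibility.** Section 3.C.1 admits five kinds of prolapse operation, ending with "minimally-invasive colpopexy (either laparoscopic or robotic-assisted laparoscopic), colporrhaphy, or colpocleisis". Its exclusions do not mention preoperative opioid use or chronic pain.
- **Expected predictors.** Section 1.3 lists preoperative opioid use, tobacco use, chronic pain, anxiety and depression, and hypothesises that "subjects with these clinical conditions will have higher postoperative opioid consumption rates". The type of operation is not on that list.
- **Data already collected.** Section 6.C.1 has the medical record and CURES searched, between surgery and the 2-week visit, for opioid prescriptions in the 30 days before surgery.
- **Primary analysis.** Section 6.I.2 compares mean tablets between arms by t-test and names no covariate or stratum. Item 4 of the same section enters N/A for further analyses of the primary outcome. Comparisons by preexisting condition (Sections 1.3 and 1.4) are separate questions and do not adjust the comparison of arms.
- **Sample size.** Section 6.I.5 says that "a sample size of 63 subjects in each arm is necessary to achieve 80% power". The target is 5 tablets between the arm means, alpha is 0.05, and the SD is given only indirectly: "This difference is equivalent to a difference of 0.5 SD".

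**The concern.** The plan names a baseline factor that it expects to raise consumption, arranges to record it for every patient, and then does not use it in the comparison that decides the trial. It also stratifies on site and does not carry site into the analysis. Whatever these factors explain stays in the residual variance, so the confidence interval is wider than the same data could give.

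Two things make this worth raising. The trial is sized at 80% power with no margin, on an SD for which the documents give no source. And if the arms turn out to differ visibly in preoperative opioid use, the plan holds no prespecified response; an adjustment added after the data are seen, in a non-blinded trial, would be open to challenge.

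**Working it through.** **Inputs from Section 6.I.5.** Difference 5 tablets; SD 10 (5 tablets equal 0.5 SD, so 5/0.5 = 10); alpha 0.05; power 80%; 63 per arm. Sidedness is not stated, but a two-sided test reproduces the plan's number.

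**1. The plan's own figure.** n per arm = 2 × (1.96 + 0.8416)² × (10/5)² = 62.8, rounded up to 63. The plan's figure is reproduced. Power at 63 is 80.1% by the normal approximation (79.5% by the noncentral t).

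**2. Standard error of the planned comparison.** SE = 10 × √(2/63) = 1.78 tablets, a 95% half-width of 1.96 × 1.78 = 3.49. If SD 10 describes this mixed population, the SE already includes chance imbalance in opioid use and operation type.

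**3. What adjustment gains.** If the covariates explain a share R² of the variance, the residual SD is 10 × √(1 − R²). Power is Φ(5/SE − 1.96), and the n needed is 62.8 × (1 − R²), rounded up. The documents give no R², so the values below are assumptions.

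| R² (assumed) | Residual SD | SE | Power at 63 per arm | n per arm for 80% |
|---|---|---|---|---|
| 0 (as planned) | 10.00 | 1.78 | 80.1% | 63 |
| 0.05 | 9.75 | 1.74 | 82.1% | 60 |
| 0.10 | 9.49 | 1.69 | 84.1% | 57 |
| 0.20 | 8.94 | 1.59 | 88.1% | 51 |
| 0.30 | 8.37 | 1.49 | 91.8% | 44 |

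**4. What such an R² would require.** For a yes/no factor with prevalence p and a difference of d tablets, R² = p(1 − p)d²/100. Neither p nor d is in the documents. Examples (assumptions):
- p = 10%, d = 5: R² = 0.02
- p = 20%, d = 5: R² = 0.04
- p = 10%, d = 10: R² = 0.09
- p = 20%, d = 10: R² = 0.16
- p = 20%, d = 15: R² = 0.36

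The upper half of the table in step 3 therefore needs a strong predictor.

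**5. Size of chance imbalance.** The SD of the between-arm difference in prevalence is √(2p(1 − p)/63): 5.3 percentage points at p = 10% and 7.1 at p = 20%. Multiplied by d, a one-SD imbalance moves the difference by 5.3% × 10 = 0.5 tablets at the low end (p = 10%, d = 10) and 7.1% × 15 = 1.1 tablets at the high end (p = 20%, d = 15). With d = 5, a shift above 1 tablet has probability under 0.1% at p = 10% and about 0.5% at p = 20%.

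**6. Validity of the unadjusted test.** Simulation of the t-test with an unbalanced prognostic factor (40,000 trials per scenario) gave a type I error of 0.050 to 0.052, power of 79 to 80% and average bias of about zero.

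**7. Timing of the covariate.** Section 6.C.1 randomises at whichever visit consent is given, as early as the consultation. Section 6.C.2 puts active participation, from consent to the 6-week visit, at 3 to 6 months. Taking 3 months as about 13 weeks, 13 − 6 = 7 weeks lie between consent and surgery, which is longer than 30 days. For such a patient the whole 30-day window falls after randomisation. In addition, the standardised postoperative prescription is issued before surgery in both arms, so the search as written could pick up the study's own prescription.

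**The case against.** The strongest case for leaving the plan alone is that an unadjusted t-test is valid here and, on the plan's assumptions, has the stated power. Steps 2 and 6 confirm both. If the documents' silence on prognostic strength hides a weak predictor, the gain is only two to four percentage points of power. That stands, and it is why this is an improvement and not an error.

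It does not remove the reason to adjust. The predictor is the plan's own, the search is already planned, and spare precision is useful where the SD is unsourced. If the SD were 12 (assumption), unadjusted power would be Φ(5/(12 × √(2/63)) − 1.96), about 65%.

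A reader might go further and infer that chance imbalance threatens the result, for instance by moving the difference by a fifth of the 5-tablet target. The documents do not support this. As a one-SD event, a 1-tablet shift needs roughly 20% prevalence together with 15 extra tablets, and 15 exceeds the whole assumed control mean ("patients who do not undergo the educational intervention will consume a mean of 10 tablets"). Whatever its size, such a shift is random error that the SE already counts.

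A reader might also infer that randomisation should be stratified by surgical route. The documents do not rank the operations by opioid need and state a route only for colpopexy. Nor is the lack of stratification on opioid use an oversight: on the written schedule, the search takes place after randomisation.

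**Conclusion.** The point holds as one of precision. The primary comparison ignores a factor on which the trial stratifies and another that the plan expects to predict the outcome. Adjusting for them would raise power from about 80% to about 82% or 84% if they explain 5% or 10% of the variance, and to about 88% or 92% if they explain 20% or 30%. These figures assume SD 10, 63 evaluable patients per arm, a two-sided 0.05 test and the stated R² values, none of which the documents supply. There is no bias, no inflated type I error and no shortfall against the plan's stated power, provided SD 10 fits this population. This is a free improvement; eligibility, sample size and randomisation need not change.

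**What to change.** Keep the eligibility criteria and site-only stratification. In Section 6.I.2, replace the t-test with a prespecified linear model (ANCOVA) of tablets consumed at 2 weeks on arm, site and preoperative opioid prescription (yes/no). The arm coefficient and its 95% confidence interval are the primary result.

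Take the covariate from the record and CURES search already planned. Count only prescriptions dated before randomisation and exclude the study's own postoperative prescription. Because some patients are randomised more than 30 days before surgery, run the search over a window that ends at randomisation; otherwise the covariate would be empty for them.

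Planned procedure group may be added as a further covariate if its categories are written down in advance. Report the unadjusted t-test as a supportive analysis.

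Cost: a short change to the analysis section, a changed date limit on an existing search, slightly more analysis work, and two or three model degrees of freedom out of 126 evaluable patients (2 × 63).
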